13.3 Interim Analysis

Involvement in this study as a participating investigator implies acceptance of potential audits or inspections, including source data verification, by representatives designated by or the Overall Principal Investigator. The purpose of these audits or inspections is to examine study-related activities and documents to determine whether these activities were conducted, and data were recorded, analyzed, and accurately reported in accordance with the protocol, institutional policy, Good Clinical Practice (GCP), and any applicable regulatory requirements.

14 DATA COLLECTION, RETENTION AND MONITORING

14.1 Data Collection Instruments

The Investigator will prepare and maintain adequate and accurate source documents designed to record all observations and other pertinent data for each subject treated with the study drug.

Study personnel at the study site will enter data from source documents corresponding to a subject's visit into the protocol-specific paper CRF when the information corresponding to that visit is available. Subjects will not be identified by name in the study database or on any study documents to be collected by the Sponsor (or designee), but will be identified by a site number, subject number and initials.

The Investigator is responsible for all information collected on subjects enrolled in this study. All data collected during the course of this study must be reviewed and verified for completeness and accuracy by the Investigator. A copy of the CRF will remain at the Investigator's site at the completion of the study.

14.2 Data Management Procedures

The data will be entered into a validated database. The Data Management group will be responsible for data processing, in accordance with procedural documentation. Database lock will occur once quality assurance procedures have been completed.

All procedures for the handling and analysis of data will be conducted using good computing practices meeting FDA guidelines for the handling and analysis of data for clinical trials.

14.3 Data Quality Control and Reporting

After data have been entered into the study database, a system of computerized data validation checks will be implemented and applied to the database on a regular basis. Query reports (Data Clarification Requests) pertaining to data omissions and discrepancies will be forwarded to the Investigators and study monitors for resolution. The study database will be updated in accordance with the resolved queries. All changes to the study database will be documented.

14.4 Archival of Data

The database is safeguarded against unauthorized access by established security procedures; appropriate backup copies of the database and related software files will be maintained. Databases are backed up by the database administrator in conjunction with any updates or changes to the database.

At critical junctures of the protocol (e.g., production of interim reports and final reports), data for analysis is locked and cleaned per established procedures.

14.5 Availability and Retention of Investigational Records

The Investigator must make study data accessible to the monitor, other authorized representatives of the Sponsor (or designee), IRB/IEC, and Regulatory Agency (e.g., FDA) inspectors upon request. A file for each subject must be maintained that includes the signed Informed Consent, HIPAA Authorization and Assent Form and copies of all source documentation related to that subject. The Investigator must ensure the reliability and availability of source documents from which the information on the CRF was derived.

All study documents (patient files, signed informed consent forms, copies of CRFs, Study File Notebook, etc.) must be kept secured for a period of two years following marketing of the investigational product or for two years after centers have been notified that the IND has been discontinued. There may be other circumstances for which the Sponsor is required to maintain study records and, therefore, the Sponsor should be contacted prior to removing study records for any reason.

14.6 Monitoring

Monitoring visits will be conducted by representatives of the Sponsor according to the U.S. CFR Title 21 Parts 50, 56, and 312 and ICH Guidelines for GCP (E6). By signing this protocol, the Investigator grants permission to the Sponsor (or designee), and appropriate regulatory authorities to conduct on-site monitoring and/or auditing of all appropriate study documentation.

14.7 Subject Confidentiality

In order to maintain subject confidentiality, only a site number, subject number and subject initials will identify all study subjects on CRFs and other documentation submitted to the Sponsor. Additional subject confidentiality issues (if applicable) are covered in the Clinical Study Agreement.

15 ADMINISTRATIVE, ETHICAL, REGULATORY CONSIDERATIONS

The study will be conducted according to the Declaration of Helsinki, Protection of Human Volunteers (21 CFR 50), Institutional Review Boards (21 CFR 56), and Obligations of Clinical Investigators (21 CFR 312).

To maintain confidentiality, all laboratory specimens, evaluation forms, reports and other records will be identified by a coded number and initials only. All study records will be kept in a locked

file cabinet and code sheets linking a patient's name to a patient identification number will be stored separately in another locked file cabinet. Clinical information will not be released without written permission of the subject, except as necessary for monitoring by the FDA. The Investigator must also comply with all applicable privacy regulations (e.g., Health Insurance Portability and Accountability Act of 1996, EU Data Protection Directive 95/46/EC).

15.1 Protocol Amendments

Any amendment to the protocol will be written by the PI. Protocol amendments cannot be implemented without prior written IRB/IEC approval except as necessary to eliminate immediate safety hazards to patients. A protocol amendment intended to eliminate an apparent immediate hazard to patients may be implemented immediately, provided the IRBs are notified within five working days.

15.2 Institutional Review Boards and Independent Ethics Committees

The protocol and consent form will be reviewed and approved by the IRB/IEC of each participating center prior to study initiation. Serious adverse experiences regardless of causality will be reported to the IRB/IEC in accordance with the standard operating procedures and policies of the IRB/IEC, and the Investigator will keep the IRB/IEC informed as to the progress of the study. The Investigator will obtain assurance of IRB/IEC compliance with regulations.

Any documents that the IRB/IEC may need to fulfill its responsibilities (such as protocol, protocol amendments, Investigator's Brochure, consent forms, information concerning patient recruitment, payment or compensation procedures, or other pertinent information) will be submitted to the IRB/IEC. The IRB/IECs written unconditional approval of the study protocol and the informed consent form will be in the possession of the Investigator before the study is initiated. The IRB/IECs unconditional approval statement will be transmitted by the Investigator to the Sponsor or designee prior to the shipment of study supplies to the site. This approval must refer to the study by exact protocol title and number and should identify the documents reviewed and the date of review.

Protocol and/or informed consent modifications or changes may not be initiated without prior written IRB/IEC approval except when necessary to eliminate immediate hazards to the patients or when the change(s) involves only logistical or administrative aspects of the study. Such modifications will be submitted to the IRB/IEC and written verification that the modification was submitted and subsequently approved should be obtained.

The IRB/IEC must be informed of revisions to other documents originally submitted for review; serious and/or unexpected adverse experiences occurring during the study in accordance with the standard operating procedures and policies of the IRB; new information that may affect adversely the safety of the patients of the conduct of the study; an annual update and/or request for re-approval; and when the study has been completed.

15.3 Informed Consent Form

Informed consent will be obtained in accordance with the Declaration of Helsinki, ICH GCP, US Code of Federal Regulations for Protection of Human Subjects (21 CFR 50.25[a,b], CFR 50.27, and CFR Part 56, Subpart A), the Health Insurance Portability and Accountability Act (HIPAA, if applicable), and local regulations.

The Investigator will prepare the informed consent form, assent and HIPAA authorization and provide the documents to the Sponsor or designee for approval prior to submission to the IRB/IEC. The consent form generated by the Investigator must be acceptable to the Sponsor and be approved by the IRB/IEC. The written consent document will embody the elements of

informed consent as described in the International Conference on Harmonisation and will also comply with local regulations. The Investigator will send an IRB/IEC-approved copy of the Informed Consent Form to the Sponsor (or designee) for the study file.

A properly executed, written, informed consent will be obtained from each subject prior to entering the subject into the trial. Information should be given in both oral and written form and subjects (or their legal representatives) must be given ample opportunity to inquire about details of the study. If appropriate and required by the local IRB/IEC, assent from the subject will also be obtained. If a subject is unable to sign the informed consent form (ICF) and the HIPAA authorization, a legal representative may sign for the subject. A copy of the signed consent form (and assent) will be given to the subject or legal representative of the subject and the original will be maintained with the subject's records.

15.4 Publications

The preparation and submittal for publication of manuscripts containing the study results shall be in accordance with a process determined by mutual written agreement among the study Sponsor and participating institutions. The publication or presentation of any study results shall comply with all applicable privacy laws, including, but not limited to, the Health Insurance Portability and Accountability Act of 1996.

15.5 Investigator Responsibilities

By signing the Agreement of Investigator form, the Investigator agrees to:

1. Conduct the study in accordance with the protocol and only make changes after notifying the Sponsor (or designee), except when to protect the safety, rights or welfare of subjects.
2. Personally conduct or supervise the study (or investigation).
3. Ensure that the requirements relating to obtaining informed consent and IRB review and approval meet federal guidelines, as stated in § 21 CFR, parts 50 and 56.
4. Report to the Sponsor or designee any AEs that occur in the course of the study, in accordance with §21 CFR 312.64.
5. Ensure that all associates, colleagues and employees assisting in the conduct of the study are informed about their obligations in meeting the above commitments.
6. Maintain adequate and accurate records in accordance with §21 CFR 312.62 and to make those records available for inspection with the Sponsor (or designee).
7. Ensure that an IRB that complies with the requirements of §21 CFR part 56 will be responsible for initial and continuing review and approval of the clinical study.
8. Promptly report to the IRB and the Sponsor (or designee) all changes in the research activity and all unanticipated problems involving risks to subjects or others (to include amendments and IND safety reports).
9. Seek IRB approval before any changes are made in the research study, except when necessary to eliminate hazards to the patients/subjects.
10. Comply with all other requirements regarding the obligations of clinical investigators and all other pertinent requirements listed in § 21 CFR part 312.

References:

16 APPENDICES

Appendix 1: Patient instructions

Appendix 2: Treatment diary

Appendix 3: Visit #1 CRF

Appendix 4: Visit #2 CRF

Appendix 5: OHIP-14

CONFIDENTIAL

This document is confidential. Do not disclose or use except as authorized.

Appendix 1**INSTRUCTIONS FOR PREPARING & USING YOUR
TOPICAL SOLUTION****WHAT YOU WILL RECEIVE**

- One 480 mL bottle of concentrated solution (5 mg/5 mL)
- 4 tablets of fluconazole 200 mg

USING YOUR SOLUTION

You will be rinsing with your solution **3 times per day**.

1. Gently shake the bottle of solution.
2. Pour 5 mL of solution into the dosing cups provided.
3. Swish the solution in your mouth for 5 minutes, then spit – DO NOT SWALLOW!
4. Do not eat or drink for 15 minutes after rinsing.

Please take one table of fluconazole once a week

CONFIDENTIAL

This document is confidential. Do not disclose or use except as authorized.

	11													
	12													
	13													
	14													

	3													
	15													
	16													
	17													
	18													
	19													
	20													
	21													
	22													
	4													

CONFIDENTIAL

This document is confidential. Do not disclose or use except as authorized.

	23																						
	24																						
	25																						
	26																						
	27																						
	28																						

CONFIDENTIAL

This document is confidential. Do not disclose or use except as authorized.

Appendix 3

DEXAMETHASONE RINSE IN MUCOLOX™ FOR THE TREATMENT OF ORAL INFLAMMATORY ULCERATIVE DISEASES

VISIT #1

Subject Name _____

[figure not shown]
[figure not shown]
Medical Record Number _____

Date of Visit _____

SUBJECTIVE DATA (Over last two weeks unless specified)

MUCOSAL PATHOLOGY

- 1. Does your mouth hurt now? Y/N
- 2. Does it hurt to swallow food or drink? Y/N
- 3. How would you rate your worst mouth sensitivity over the last week?

No sensitivity

Worst sensitivity

CONFIDENTIAL

This document is confidential. Do not disclose or use except as authorized.

[figure not shown]
[figure not shown]
4. Do you avoid any foods because they make your mouth hurt?

- 0 = Not at all
- 1 = Slightly
- 2 = Moderately
- 3 = Quite a bit
- 4 = Extremely

If “yes”, what types of foods?

- a. Spicy foods
- b. Acidic foods
- c. Salty foods
- d. Hard/crunchy/crusty foods
- e. Other:

5. Do you feel that your oral intake (what you eat) is limited by your oral condition? Y/N

Not limited at all

Severely limited

Score: _____

If “Yes”, how limited do you feel it is?

- a. Partial limitation
- b. Severe limitation

6. Have you been bothered by ulcers in the mouth?

- 0 = Not at all
- 1 = Slightly
- 2 = Moderately
- 3 = Quite a bit
- 4 = Extremely

CONFIDENTIAL

This document is confidential. Do not disclose or use except as authorized.

OBJECTIVE DATA (REU score)

Site	Reticular area			Erythematous area			Ulcerative area			
	0	1	2	0	1	2	0	1	2	3
Upper/lower labial mucosa	0	1	0	1	2	3	0	1	2	3
Right buccal mucosa	0	1	0	1	2	3	0	1	2	3
Left buccal mucosa	0	1	0	1	2	3	0	1	2	3
Dorsal tongue	0	1	0	1	2	3	0	1	2	3
Ventral tongue	0	1	0	1	2	3	0	1	2	3
Floor of mouth	0	1	0	1	2	3	0	1	2	3
Hard palate mucosa	0	1	0	1	2	3	0	1	2	3
Soft palate/tonsillar pillars	0	1	0	1	2	3	0	1	2	3
Maxillary gingiva	0	1	0	1	2	3	0	1	2	3
Mandibular gingiva	0	1	0	1	2	3	0	1	2	3
Total										

(R: 0 = not present, 1 = present; E & U: 0 = not present, 1 = <1cm², 2 = 1 - 3cm², 3 = >3cm²)

Total Score:

Total Weighted Score:

PHOTOGRAPHS TAKEN (circle): YES NO

CONFIDENTIAL

This document is confidential. Do not disclose or use except as authorized.

Appendix 4

DEXAMETHASONE RINSE AND MUCOLOX™ FOR THE TREATMENT OF ORAL INFLAMMATORY ULCERATIVE DISEASES

VISIT #2

Subject Name _____

Medical Record Number _____

[figure not shown]
Date of Visit _____

SUBJECTIVE DATA (Over last one week unless specified)

MUCOSAL PATHOLOGY

- 1. Does your mouth hurt now? Y/N
- 2. Does it hurt to swallow food or drink? Y/N

3. How would you rate your worst mouth sensitivity over the last week?

No sensitivity

Worst sensitivity

4. Do you avoid any foods because they make your mouth hurt?

- 0 = Not at all
- 1 = Slightly
- 2 = Moderately
- 3 = Quite a bit
- 4 = Extremely

[figure not shown]
[figure not shown]
CONFIDENTIAL

This document is confidential. Do not disclose or use except as authorized.

If “yes”, what types of foods?

- a. Spicy foods
- b. Acidic foods
- c. Salty foods
- d. Hard/crunchy/crusty foods
- e. Other:

5. Do you feel that your oral intake (what you eat) is limited by your oral condition? Y/N

Not limited at all

Severely limited

Score: _____

If “Yes”, how limited do you feel it is?

- a. Partial limitation
- b. Severe limitation

[figure not shown]
6. Have you been bothered by ulcers in the mouth?

- 0 = Not at all
- 1 = Slightly
- 2 = Moderately
- 3 = Quite a bit
- 4 = Extremely

7. Rate your level of comfort while rinsing with the topical therapy:

[figure not shown]
CONFIDENTIAL

This document is confidential. Do not disclose or use except as authorized.

[figure not shown]
Score: _____

8. Rate the taste of the topical treatment:

Score: _____

9. Rate how your mouth feels since starting topical therapy:

Score: _____

10. Overall, since beginning topical therapy, my mouth is: (Check one)

- Very much better
- Moderately better

CONFIDENTIAL

This document is confidential. Do not disclose or use except as authorized.

- A little better
- About the same
- A little worse
- Moderately worse
- Very much worse

CONFIDENTIAL

This document is confidential. Do not disclose or use except as authorized.

OBJECTIVE DATA

Site	Reticular area			Erythematous area			Ulcerative area			
	0	1	2	0	1	2	0	1	2	3
Upper/lower labial mucosa	0	1	2	0	1	2	0	1	2	3
Right buccal mucosa	0	1	2	0	1	2	0	1	2	3
Left buccal mucosa	0	1	2	0	1	2	0	1	2	3
Dorsal tongue	0	1	2	0	1	2	0	1	2	3
Ventral tongue	0	1	2	0	1	2	0	1	2	3
Floor of mouth	0	1	2	0	1	2	0	1	2	3
Hard palate mucosa	0	1	2	0	1	2	0	1	2	3
Soft palate/tonsillar pillars	0	1	2	0	1	2	0	1	2	3
Maxillary gingiva	0	1	2	0	1	2	0	1	2	3
Mandibular gingiva	0	1	2	0	1	2	0	1	2	3
Total										

(R: 0 = not present, 1 = present; E & U: 0 = not present, 1 = <1cm², 2 = 1 - 3cm², 3 = >3cm²)

Total Score:

Total Weighted Score:

PHOTOGRAPHS TAKEN (circle): YES NO

CONFIDENTIAL

This document is confidential. Do not disclose or use except as authorized.

CONFIDENTIAL

This document is confidential. Do not disclose or use except as authorized.

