PRIMARY OBJECTIVE	The primary objective of this study is to determine the clinical efficacy and tolerability of compound dexamethasone at 0.5 mg/5 mL in Mucolox™ for the treatment of Oral Inflammatory Ulcerative Diseases as measured by a reduction in oral symptoms between patients treated with compounded dexamethasone 0.5mg/5ml solution in Mucolox™ (group A) and patients treated with topical commercial dexamethasone 0.5mg/5ml solution only (group B).
SECONDARY OBJECTIVES	The secondary objectives are: 
 • To determine the clinical improvement in clinician-reported outcome measures achieved by treatment with topical compounded dexamethasone at 0.5 mg/5 mL in Mucolox™ compared to commercial dexamethasone 0.5mg/5ml solution alone. • To assess the tolerability of Oral Inflammatory Ulcerative Diseases as measured with the 14-item Oral Health Impact Profile (OHIP-14).
NUMBER OF SUBJECTS	30
SUBJECT SELECTION	Inclusion Criteria:

CRITERIA
	
Age 18 years and older.
 
Patients with symptomatic biopsy proven Oral Inflammatory Ulcerative Diseases (worst VAS sensitivity score ≥ 7 over the last week).
 
Ability to understand and the willingness to sign a written informed consent document.
 
Exclusion Criteria: Patients already on topical or systemic steroids.
 
Inability to comply with study instructions.
 
Uncontrolled intercurrent illness or psychiatric illness/social situations that would limit compliance with study requirements.
 
VAS sensitivity score < 7.
 
Pregnant women. A urine pregnancy test will be performed for women of child bearing potential.
 
Allergy to fluconazole
 
Patients on medications that have a strong interaction with fluconazole
 
Patients with advanced liver disease

TEST PRODUCT, DOSE, AND ROUTE OF ADMINISTRATION
	
Dexamethasone 0.5 mg/5mL in Mucolox compounded oral solution swish and spit TID for 4 weeks

CONTROL PRODUCT, DOSE AND ROUTE OF ADMINISTRATION
	
Dexamethasone 0.5 mg/5mL (NDC 00054-3177-63; Roxane Laboratories, Columbus, OH 43216-6532) oral solution swish and spit TID for 4 weeks

DURATION OF SUBJECT PARTICIPATION AND DURATION OF STUDY
	
Subjects will be on study for up to 28 days
 
Screening: day 0
 
Treatment: 28 days
 
Follow-up: Day 28 \pm 5 days
 
The total duration of the study is expected to be 4 weeks.

CONCOMITANT MEDICATIONS	Allowed: all Prohibited: none

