8.3 Formulation of Test and Control Products

8.3.1 Mucolox™

Description

Mucolox™ (PCCA, Houston, TX 77099) is a mucoadhesive polymer designed to improve mucoadhesion and prolong retention of medications at application sites within the oral mucosa. The composition of Mucolox™ is outlined in the table below.

Ingredient Name	INCI Name/Technical Name	Classification	FDA Reference
Potassium Sorbate NF	Potassium Sorbate	Subpart D – Chemical Preservatives	21 CFR 582.3640
Sodium Benzoate NF	Sodium Benzoate	Subpart D – Chemical Preservatives	21 CFR 582.3733
Glycerin USP (Natural)	Glycerin	Subpart B – General Purpose Food Additive	21 CFR 582.1320
Edetate Disodium USP Dihydrate	Disodium EDTA	FDA has no questions regarding intended use.	GRN000363
Pullulan	Pullulan	FDA has no questions regarding intended use in certain foods.	GRN000099
Tamarindus Indica Seed Polysaccharide	Tamarindus Indica Seed Polysaccharide	FDA has no questions regarding intended use.	GRN000503
Isomalt	Isomalt	Self-Determined GRAS (1996)	GRN6G0321
Simethicone USP	Simethicone	Used in Various Routes, Dosage Forms and Maximum Potencies	UNII: Multiple (Mixture)
Sodium Hyaluronate	Sodium Hyaluronate	Used in Various Routes, Dosage Forms and Maximum Potencies	UNII: YSE9PPT4TH
Poloxamer 407	Poloxamer 407	Used in Various Routes, Dosage Forms and Maximum Potencies	UNII: TUF2IVW3M2
Zea Mays (Corn) Starch	Zea Mays (Corn) Starch	Used in Various Routes, Dosage Forms and Maximum Potencies	UNII: O8232NY3SJ
Carbomer	Carbomer	Used in Various Routes, Dosage Forms and Maximum Potencies (Type: Proprietary)	UNII: Type Proprietary
Water	Water	N/A	UNII: 059QF0K00R

Compatibility

N/A

Handling

There are no special handling requirements.

Availability

Compounded dexamethasone solution in Mucolox™ will be dosed at a concentration of 0.5 mg/5mL and dispensed through the UCSF Investigational Drugs Services Pharmacy. The prescription for the patients in ARM B (dexamethasone) will also be dispensed through the UCSF Investigational Drugs Services Pharmacy.

Preparation

Study subjects will be given a kit with the following, including detailed written instructions (see Appendix 1):

ARM A

- A four week supply of compounded dexamethasone solution in Mucolox™ will be dispensed, with extra for error and spillage, which will be rounded to 480 mL bottle at a concentration of 0.5 mg/5mL.
- Small dosing cups

Administration

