8.4 Dexamethasone solution

Description

Dexamethasone (NDC 00054-3177-63; Roxane Laboratories, Columbus, OH 43216-6532) is a synthetic adrenocortical steroid commercially available as a 0.5mg/5mL solution. It is stable in air and practically insoluble in water.

- The molecular weight is 392.47.
- The molecular formula is $C_{22}H_{29}FO_5$
- The structural formula is:

Each 5 mL of oral solution contains 0.5 mg of dexamethasone and citric acid, disodium edetate, flavoring, glycerin, methylparaben, propylene glycol, propylparaben, sorbitol and water.

Storage and Stability

Dexamethasone solution is stable at room temperature for 30 days after opening per package insert.

Compatibility

N/A

Handling

There are no special handling requirements.

Availability

Dexamethasone 0.5mg/5mL solution will be dispensed through the UCSF Investigational Drugs Services Pharmacy.

Preparation

Study subjects will be given a kit with the following, including detailed written instructions (see Appendix 1):

ARM B

- A four-week supply of dexamethasone solution will be dispensed, with extra for error and spillage, which will be rounded to 480 mL bottle at a concentration of 0.5 mg/5mL.
- Small dosing cups

Administration

Subjects will be instructed to rinse with 5 ml of the prescribed dexamethasone 0.5mg/5ml solution (ARM B) for 5 minutes. After 5 minutes, subjects will be instructed to expectorate and to not eat or drink for 15 minutes after. The rinses will be completed three times per day, equally spaced during awake hours. If a study rinse is missed, subjects will be asked to attempt to make up for the missed rinse later the same day, to maintain four rinses per day. If necessary, for example, two consecutive 5 minute rinses can be completed at night before bed. This does not pose any known safety risk.

Ordering

Dexamethasone solution will be ordered through the UCSF Investigational Drugs Services Pharmacy.

Destruction and Return

Patients should not continue to use any unused study supply once they have completed the study. It should be returned to the investigator for destruction.

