9.3 Study Agents Administration

The Investigator or co-investigators will prescribe the study drug in the clinic and instruct the patient on study drug use. Both dexamethasone compounded 0.5mg/5ml solution in Mucolox™ and commercial dexamethasone solution will be dosed topically at a concentration of 0.5 mg/5mL.

A four week supply will be dispensed. The treatment instructions will be to rinse and spit (NOT swallow) with one teaspoon (5 mL) of the solution, three times a day for 5 minutes at a time, and not to eat or drink for 15 minutes afterwards. Subjects will maintain a diary (Appendix 2) and record each dose, the length of time rinsing, and any adverse effects.

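### The patient sheet overstates the bottle strength tenfold, and the missed-rinse rule names four rinses a day under a three-a-day regimen; both are wrong as written, with small consequence

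*Combined protocol and SAP*

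**What the plan says.** **Strength.** Appendix 1 carries the title "INSTRUCTIONS FOR PREPARING & USING YOUR" (topical solution) and tells the patient to expect "One 480 mL bottle of concentrated solution (5 mg/5 mL". Its steps go from shaking the bottle to "Pour 5 mL of solution into the dosing cups provided", with no diluent and no dilution. Sections 8.3.1 (Arm A) and 8.4 (Arm B) both put this sheet in the kit: "Study subjects will be given a kit with the following, including detailed written instructions (see Appendix 1".

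The dosing sections give a different strength:
- Synopsis, test product: "Dexamethasone 0.5 mg/5mL in Mucolox compounded oral solution swish and spit TID for 4 weeks".
- Sections 8.3.1 and 8.4, Preparation: a four-week supply "which will be rounded to 480 mL bottle at a concentration of 0.5 mg/5mL".
- Section 8.4, Description: the Arm B product is "commercially available as a 0.5mg/5mL solution".
- Section 9.2.4, regimen table: 0.1 mg/mL and 0.5 mg per 5 mL rinse in both arms.
- Section 9.3, naming both products: "commercial dexamethasone solution will be dosed topically at a concentration of 0.5 mg/5mL".

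**Frequency.** The Administration paragraphs of Sections 8.3.1 and 8.4 set three rinses a day. The next sentence says a missed rinse should be made up later that day in order to keep to four a day, and offers two back-to-back rinses at bedtime as an example. The synopsis, Sections 2.1.1, 9.2.4 and 9.3, and Appendix 1 all say three a day. Appendix 1 has no missed-rinse rule.

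**The concern.** The sheet is the written instruction patients take home, and it misstates a corticosteroid's strength tenfold. The word *concentrated*, together with *preparing* in the title, could lead a patient or a staff member to look for a dilution step that does not exist. A sheet that disagrees with the dispensed bottle also leaves the reader to work out which one is right.

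The make-up sentence is the protocol's only rule for a missed rinse, it appears in both arms, and its number contradicts the sentence before it. Section 12 counts non-compliance with the study drug regimen as a protocol violation, so the regimen should have a single number.

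At worst, the delivered dose would differ from the planned one: tenfold if anyone acted on the printed strength, or by one extra rinse on make-up days if four were taken literally.

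**Working it through.** **Inputs**
- Volume per rinse: 5 mL (Sections 8.3.1, 8.4, 9.2.4, 9.3 and Appendix 1).
- Planned strength: 0.5 mg/5 mL = 0.1 mg/mL (Section 9.2.4).
- Strength printed on the sheet: 5 mg/5 mL = 1.0 mg/mL (Appendix 1).
- Planned frequency: 3 a day. Make-up target: 4 a day (Sections 8.3.1 and 8.4).
- Treatment: 28 days. Bottle: 480 mL, including extra for error and spillage.

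**Step 1. The plan's own figure.** Section 2.1.1 gives a maximum of 10.5 mg/week if everything were absorbed. 5 mL × 0.1 mg/mL × 3 × 7 = 10.5 mg. It reproduces. The bracketed arithmetic there ends in 10.5 g, which is a unit slip.

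**Step 2. Strength.** 1.0 ÷ 0.1 = 10. If the bottle really held what the sheet says, 5 mL three times a day would be 5 mg per rinse, 15 mg a day and 105 mg a week. Nothing in the plan has such a bottle dispensed, and Arm B is a commercial product at 0.5 mg/5 mL. The factor of 10 is on paper only.

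**Step 3. Is it a concentrate meant for dilution?** Use at three undiluted 5 mL rinses a day is 5 × 3 × 28 = 420 mL, leaving 480 − 420 = 60 mL spare. That matches a ready-to-use four-week bottle with an allowance for spillage.

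**Step 4. Which frequency is intended?** Four a day throughout would need 5 × 4 × 28 = 560 mL, and a 480 mL bottle would last 480 ÷ 20 = 24 days. The supply therefore supports three a day.

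**Step 5. Make-up rule.**
- Natural reading: 2 rinses taken + 1 made up = 3, so 3 × 0.5 = 1.5 mg. No change. The bedtime example also fits three.
- Literal reading, that day: 4 × 0.5 = 2.0 mg against 1.5 mg, which is +0.5 mg (+33%).
- Literal reading, a week with one such day: 6 × 1.5 + 2.0 = 11.0 mg against 10.5 mg (0.5 ÷ 10.5 = +4.8%).
- Literal reading, every day of the week: 7 × 2.0 = 14.0 mg (+33%). The documents give no missed-rinse frequency, so 11.0 to 14.0 mg is the range for a week with one to seven such days.

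**Step 6. Context.** Section 1 (chronic graft-versus-host disease) cites 4 to 6 rinses a day of the same-strength solution. At an assumed 5 mL per rinse, since no volume is given there, that is 2.0 to 3.0 mg a day or 14.0 to 21.0 mg a week. A literal make-up day sits at the bottom of the daily range, and the 11.0 mg week is below the weekly range.

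**The case against.** The strongest reply is that this is proofreading. The documents settle both values: the regimen table spells out 0.5 mg per rinse and three a day, the dispensing text fixes the bottle at 0.5 mg/5 mL, and the bottle volume fits only three a day. The printed strength sits in a list of kit contents, not among the steps, and every step the patient follows is right. Sections 8.3.1 and 8.4 use the heading Preparation for kit contents alone, so *preparing* is a weak cue to dilute. Under Section 9.3 the investigators also instruct the patient in clinic. The four-a-day wording is the same in both arms and is absent from the patient sheet. The weekly figure depends on how often rinses are missed, which is unknown, and the comparison with 4 to 6 rinses a day comes from guidance for one of the enrolled diseases only.

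Nearly all of this stands, and it is why the consequence is small. The intended values can be recovered, and removing *preparing* is the least important of the edits. But being recoverable does not make the text correct. A sheet handed to patients prints the wrong strength for their drug, and the only missed-rinse rule prints the wrong count.

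**Conclusion.** The point holds, as a minor one. Appendix 1 states ten times the strength used in every dosing section, and Sections 8.3.1 and 8.4 state a make-up target of four under a regimen of three. No harm, tenfold dispensing or difference between the arms is shown, and there is no effect on endpoints, analysis, sample size or supply. The compliance cut-off in Section 12 (fewer than 2 uses a day for more than 2 weeks) is also unaffected.

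This rests on the pharmacy dispensing 0.5 mg/5 mL as Sections 8.3.1 and 8.4 specify, and on patients measuring 5 mL as the sheet says. If Arm A were compounded from the sheet instead, that arm alone would receive ten times the planned dose. Nothing in the plan suggests this would happen. The 10.5 mg/week in Section 2.1.1 is a full-absorption calculation, not a dose limit, so a literal make-up week of 11.0 mg breaches nothing. The 10.5 g slip carries no weight in this conclusion.

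**What to change.** - Appendix 1: change the strength to 0.5 mg/5 mL, delete *concentrated*, delete *preparing &* from the title, and reissue the sheet.
- Sections 8.3.1 and 8.4: change the make-up target from four rinses a day to three.
- Section 2.1.1, in the same amendment: change 10.5 g to 10.5 mg.

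The cost is six small wording edits (3 + 1 + 1 + 1) in one amendment and a reissued one-page sheet. Nothing needs recomputing: the corrected text gives 0.5 mg per rinse, 1.5 mg a day, 10.5 mg a week and 420 mL over 28 days, as already planned.
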